In response to this critical public health issue, we propose to study Asthma Link, which is a low-cost, low-intensity community-clinical based model of supervised asthma therapy in schools. Asthma Link is an established, ongoing clinical program that promotes the adoption of the evidenced-based practice of school-supervised asthma therapy in real world settings.

Asthma Link connects the three groups that play vital roles in the health of school-aged children with asthma: pediatric practices, school nurses, and families. Pediatricians identify and enroll children with poorly controlled asthma and medication non-adherence as part of their routine practice. They send the school nurse an order for daily, supervised inhaled steroid administration at school. Families bring the prescribed inhaler to school. The school nurse supervises the child's inhaler administration and provides adherence education, as part of her daily routine, to ensure adherence and proper inhaler/spacer technique. Ongoing communication occurs between the pediatric practice, the school nurse and families throughout the school year. Asthma Link is based on prior research studies that demonstrate the safety and efficacy of school-supervised asthma therapy. The goal of Asthma Link is for school-supervised asthma therapy to operate in a real-world setting, delivered by pediatricians, school nurses and families within their current routines and relying on minimal resources and no research staff.

The goal of the proposed study is to examine the effectiveness and implementation of Asthma LinkTM in sustainable real-world practice.

Preliminary Data:

The current proposed study builds from our prior research, which has informed the proposed study. To initially test Asthma LinkTM, we performed a small pre/post study (SEE IRB DOCKET # H00010546_2) of 84 children enrolled in Asthma LinkTM (mean age 10 years, 95% Medicaid insurance, 67% Latino, 19% Black). We observed that children enrolled in Asthma LinkTM experienced a 54% decline in emergency room visits, a 95% decline in hospital admissions and a 46% decline in rescue medication use over a one-year follow-up period ($p<0.001$),¹⁷ demonstrating that Asthma LinkTM merits further rigorous evaluation. Additionally, in order to examine the barriers and facilitators to Asthma LinkTM real-world implementation, (SEE IRB DOCKET # H00012920_1), we are interviewing program stakeholders which include school

INVESTIGATOR STUDY PLAN

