10. STUDY ENDPOINTS*

Please see below table describing the primary and secondary outcome measures

SN=School Nurse

MP=Medical Provider

AC=Asthma Champion

Study Assessments, Measures and Data Collection Timing

Variable	Measure/Instrument
Designed for and Delivered to pediatric practice staff, school staff, and parent-child dyads Administered by Research coordinator	
AIM 1: Primary Feasibility Outcomes for Asthma Link™ research protocol (cluster RCT)	

INVESTIGATOR STUDY PLAN

Participation/Recruitment	# of screened and eligible participants; # refusing to participate; reason(s) for refusal
Retention	# of dropouts; subjects lost to follow-up; reason(s) for dropping out
Program usage/Intervention Fidelity (degree to which using program)	
 Checklist for pediatric practice staff to assess % of eligible children enrolled (see Pedi Practice checklist) School nurse report of % enrolled students receiving supervised therapy (see SN checklist) School nurse checklist of each enrolled child attending daily school nurse sessions and his/her family bringing medicine to school (see SN checklist)
AIM 1: Secondary Asthma Health Outcomes	
Asthma symptoms	
 Asthma Control Test (see Parent surveys), validated maximum symptom days, validated
ED visits, Admissions, Oral steroids, Medication Adherence	
 Parent report (see Parent surveys) and electronic medical record review Pharmacy refill data
Spirometry	
 Portable Spirometer (PIKO), validated⁵⁷ to assess Forced Expiratory Volume in 1sec
School absences	
 Parent and school nurse report (see Parent surveys and SN checklist)
AIM 2: Process Outcomes for Asthma Link™ Intervention Protocol	
Acceptability	
 Acceptability rating scale (5 point Likert scale) to rate each component of the Asthma Link™ intervention (see Parent, SN, MP, AC surveys)

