11. PROCEDURES INVOLVED*

Randomization. Two groups of two practices (4 practices in total) will be matched based on comparable size and percent of minority patients. Within each pair, practices will be randomly allocated to Asthma Link or the comparison condition, using a computerized function. This will result in two practices randomized to the Asthma Link condition and two practices randomized to the Enhanced Usual Care comparison condition.

Recruitment will be performed from each practice site until the target n=72 parent-child dyads (18 per site) are recruited. (see section 13 on “Sample size calculation”) Recruitment will begin during the 2021-2022 academic school year.

Procedure Steps:

1. Research coordinator (RC) identifies potentially eligible patients (children aged 6-17 years (enrolled in grade 1-12) years and prescribed a daily inhaled corticosteroid per medical record from most recent visit scheduled for a clinic visit) through the practice's office scheduling and medical record system (e.g., Epic). RC will also collect that patient's name, DOB, mailing and email addresses, phone number, insurance type (as a proxy for socioeconomic status), list of

INVESTIGATOR STUDY PLAN

medications, number of emergency room visits, number of hospital admissions and number of oral steroid courses for asthma relief.

2. RC creates a Lilac Form for any potentially eligible patients as described above. (Lilac form is an indicator to the medical provider seeing the patient that this patient is potentially eligible for study.)

3. Asthma Link condition: As part of clinical practice, medical provider will determine if patient is struggling with taking daily asthma medicine. If YES, then will introduce Asthma Link by saying “There is a clinical program that allows for your child to receive their daily asthma medicine at school supervised by the school nurse.” Child can be enrolled in Asthma Link per the usual clinical steps (see Asthma Link steps).

- After they are enrolled in Asthma Link, medical provider will give family one-page description of study (see Flyer) and state “Researchers at UMass are performing a study of children who are participating in Asthma Link, would you be interested in hearing more?”

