3a. Enhanced Usual Care comparison condition: Medical provider will determine if patient is struggling with taking daily asthma medicine, if YES, the provider will give family a one-page description of study (see Flyer) and state “Researchers at UMass are performing a study of children with asthma to learn about how to support them in taking their every day asthma medicine, would you be interested in hearing more?”

- Attached to the “Flyer” will be the Authorization to Contact form. (see Authorization to Contact form)
- If the parent agrees, the Lilac form with the family’s information is faxed to the Research Coordinator. The pediatric office will fax this form with a confidential cover form.
- The fact sheet will be mailed to the parent with a letter saying that the Research Coordinator will call or text them (see Fact Sheet).
- The Research Coordinator will only call the parent five times. The first and third time a message will not be left, but a text message will be sent stating “This is X from Asthma Link, can I call you at TIME?” The second, fourth, and fifth time a message will be left saying “This is X from the University of Massachusetts Medical School. I am calling about the material on Asthma Link I sent you. Please call me back at X.”
- A phone screen will be conducted to ensure study inclusion criteria (see phone script).
- The Research Coordinator will obtain informed consent from eligible participants, including parental permission for their child to participate, child assent to participate, and parental consent to participate. (see sections 30, 31 on Consent)
- After all questions are answered regarding the study by the parent, the Research Coordinator will send the baseline survey via email to the participant to be completed by the parent and child together or will complete the survey over the phone with the child and parent.
- The Research Coordinator will then access the child’s medical record and obtain the discharge summaries, the emergency service records, the office/clinic notes, the problem list, the pulmonary studies, the child’s list of medications, and the child’s height and weight (to help interpret the spirometry data).
- The Research Coordinator will then call the child’s pharmacy to obtain refill history for their daily ICS inhaler.

INVESTIGATOR STUDY PLAN

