Portable Spirometry: At baseline, 3, 6, and 12 months the child will perform spirometry in the school nurse's office. The Research Coordinator will perform portable spirometry in the school at the time that the student normally reports to the nurse for their daily asthma medication so as not to disrupt the child's school activities. Given that the spirometry test takes less than 3 minutes to complete for each child, we are confident that it will not pose a disruption to the child's school activities. The Research Coordinator will enter the spirometry data into RedCap for each participant without downloading any data.

School absence data will be collected through school nurse report and will be recorded from the school nurse on the School Nurse checklist and faxed to the Research Coordinator.

Asthma Link Condition: Those practices that are randomized to the Asthma Link group will receive pediatric pulmonologist delivered trainings for pediatric practices on behavioral strategies to help promote asthma medication adherence and a 1 hour training on the Asthma Link clinical program and how to enroll children in Asthma Link (reviewing the steps of this clinical program- see "Asthma Link Clinical Program Steps") and carry out this evidenced-based program in the context of their clinical practice (reviewing the steps to Asthma Link and answering any questions they may have).

Comparison Condition: Those practices that are randomized to the Enhanced Usual Care Comparison Group will receive pediatric pulmonologist delivered trainings for pediatric practices on behavioral strategies to help promote asthma medication adherence. These include training to counsel patients on the strategies such as the placement of cell phone alarms to remember to take their daily medicine and placement of an elastic band around the inhaler and the toothbrush so that a child always remembers to take their daily inhaler before brushing their teeth. We thought it ethically important to provide more than just usual care to the 2 pediatric practices assigned to the comparison condition.

Families who agree to participate in the study from either the Asthma Link or Enhanced Usual Care practices will receive a mailed "Asthma Workbook" to aid in their understanding of asthma, support their asthma care and help with daily medicine adherence (See Asthma Workbook)

INVESTIGATOR STUDY PLAN

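### The only spirometry occasion in the plan is the daily nurse dosing visit, which by design only Asthma Link children have, so FEV1 test conditions could differ by arm

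*Combined protocol and SAP*

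**What the plan says.** Section 11 (Procedures Involved), in the paragraph on portable spirometry, gives the schedule and place without naming an arm: "At baseline, 3, 6, and 12 months the child will perform spirometry in the school nurse's office". The next sentence gives the only timing rule: the research coordinator tests at school "at the time that the student normally reports to the nurse for their daily asthma medication". The stated reason is to avoid disrupting the school day.

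The daily nurse visit belongs to one arm. Section 5 (Background) says of the practices using Asthma Link: "They send the school nurse an order for daily, supervised inhaled steroid administration at school". In Section 11, step 3, under the Asthma Link condition, the provider introduces the program with the words "There is a clinical program that allows for your child to receive their daily asthma medicine at school supervised by the school nurse".

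The comparison condition in Section 11 is training for the practice in adherence counselling: phone alarms, and an elastic band around inhaler and toothbrush so that the child "remembers to take their daily inhaler before brushing their teeth". Its recruitment step (3a) has the provider hand over a flyer and say "Researchers at UMass are performing a study of children with asthma to learn about how to support them in taking their every day asthma medicine". Neither text contains a nurse order or a dose at school.

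Section 10 (Study Endpoints) lists portable spirometry "to assess Forced Expiratory Volume in 1sec". Section 4 (Objectives) makes the between-arm difference in spirometry values a secondary trial outcome. Section 13 (Data Analysis and Management) calls the health-outcome analyses exploratory, and says that the pilot will supply effect size estimates which, with published data, will help to size the larger trial.

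**The concern.** A measurement should be taken under the same conditions in both arms. Here the one stated occasion is itself part of the intervention. Asthma Link tests are anchored to a dosing visit, and comparison tests have no stated anchor. Time of day and time since the last inhaler use could then differ with allocation.

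A shift that follows allocation goes straight into the between-arm difference. A larger sample makes the estimate more precise but leaves the shift in place. If the times are not recorded, nobody can check afterwards whether the conditions matched, or adjust for it.

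At stake are the FEV1 comparison and the FEV1 effect size passed to the larger trial. The procedure itself is also at stake: Section 13 counts the feasibility of the assessment procedures among the things the pilot is to establish, and a timing rule that does not fit one arm should not be carried forward as it stands.

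**Working it through.** There is no figure in the plan to reproduce: the documents give no SD, effect size, alpha or power for FEV1. The check is to apply the timing rule to each arm.

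| Question | Asthma Link | Enhanced Usual Care |
|---|---|---|
| Daily nurse visit for medication provided by the design? | Yes (Section 5; Section 11, step 3) | No (Section 11, step 3a and comparison condition) |
| Test occasion stated? | Yes, that visit | None that applies |
| Clock window stated? | No | No |
| Test before or after that day's inhaler use? | Not stated | Not stated |
| Time of test, last ICS use or last rescue use to be recorded? | Not stated | Not stated |

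**Step 1: how many children are affected.** Section 13 plans 72 dyads, 36 per condition. The rule has no occasion to attach to for 36/72 = 50% of the planned sample, unless a comparison child happens to receive a daily dose from the nurse in ordinary care. The documents neither provide for that nor exclude it.

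**Step 2: whether baseline rescues the comparison.** A constant shift present at both baseline and follow-up would cancel in a change from baseline. Section 13 specifies no such analysis for FEV1; it names a t-test, a nonparametric counterpart or Poisson regression between arms. The DSMB part of Section 14 says that Asthma Link families join the study after joining the program. Their baseline test may therefore fall at a dosing visit or before regular attendance begins, and the documents do not say which. Cancellation cannot be assumed.

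**Step 3: whether a size can be derived.** The bias in standard errors is shift / SE. With 36 per arm and 18 per practice, the design effect is 1 + (18 − 1) × ICC, and the SE of the standardised difference is sqrt(2 × design effect / 36).

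- ICC 0.01 (used for retention in Section 13): design effect 1.17; SE = sqrt(2 × 1.17 / 36) = 0.255 SD.
- ICC 0.05 (called conservatively large there): design effect 1.85; SE = sqrt(2 × 1.85 / 36) = 0.321 SD.

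These ICCs are borrowed, as none is given for FEV1. The numerator, the shift in FEV1 due to different test conditions, appears nowhere in the documents, and neither does its sign. No size follows.

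**The case against.** The strongest reply is that the plan is silent on comparison-arm timing and does not prescribe different timing. Nor does it say at what hour Asthma Link children see the nurse. A reader might infer that comparison children are tested whenever suits the school and that conditions therefore differ systematically; the documents support only that they could differ. The Asthma Link program steps and the school nurse checklist are cited but not reproduced, and might narrow the gap. This part of the reply stands. It does not change the fact that the one occasion stated for all children exists by design in one arm only.

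Three further limits also stand.

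- **Nurse coaching.** It is tempting to add coaching on inhaler technique as a third difference in test conditions. Section 5 makes it part of the intervention, so any FEV1 gain through technique is treatment effect.
- **The SD.** A constant shift between arms leaves the within-arm SD unchanged, so the documents do not support a claim that the SD for the larger trial is biased.
- **Position relative to the dose.** The supervised drug is a daily preventive steroid, and nothing in the documents says that one dose changes FEV1 within minutes. The point does not rest on that. It rests on the absence of a common, recorded test occasion.

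Finally, FEV1 is one of several secondary outcomes, and the primary trial outcomes are recruitment, retention and fidelity. Section 13 itself warns that small pilots give imprecise effect sizes, and it will combine the results with a clinically meaningful effect and earlier trials. That limits the consequence without removing the reason for a common rule.

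**Conclusion.** The point holds in a limited form. The plan ties FEV1 testing in all children to a visit that its design provides only in the Asthma Link arm, leaves the comparison occasion unstated, and calls for no record of test time or recent inhaler use. This can bias the exploratory FEV1 comparison and the FEV1 effect size carried forward. It does not touch the primary feasibility outcomes.

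The size and direction are unknown. A reader might try to supply a size by assuming a shift of 2 to 5 points of % predicted and an SD of 12 to 20. With SE = SD × sqrt(2/36), that gives 2/4.71 = 0.42 to 5/2.83 = 1.77 standard errors. The documents do not support this range: both inputs are invented, and the SE ignores clustering by practice. Dividing by sqrt(1.17) or sqrt(1.85) already lowers it to 0.39–1.63 or 0.31–1.30, and the assumed inputs remain.

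The conclusion assumes that the unseen program steps and checklists do not already set a common test time. It is a cheap improvement, not a fault that invalidates the pilot.

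**What to change.** In the portable spirometry paragraph of Section 11:

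1. Replace the timing rule with one school-day testing window that children in both arms can meet, applied at baseline, 3, 6 and 12 months.
2. State one rule, identical in both arms, for the test's position relative to that day's inhaler use. The rule governs when the test is done and leaves unchanged when any child is treated. Placing the test before the school dose in the Asthma Link arm alone would not be enough: a comparison child may already have used the inhaler at home that morning, so the interval from dose to test could still differ.
3. Record three fields at each test: time of test, time of last ICS use and time of last rescue inhaler use. Remaining differences can then be checked or adjusted for.

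The cost is a sentence or two, three data fields and less flexible scheduling. The last is not trivial: Section 25 allows up to 100 dyads and up to 50 school nurses, so there could be up to 100 × 4 = 400 tests across many schools, and Section 23 provides a research coordinator at 0.6 FTE. The window should be wide enough to be workable; the recorded times then show how well it was kept.

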12. DATA AND SPECIMEN BANKING*

N/A

13. Data Analysis and Management*

Sample size calculation

In order to obtain a sample size of 72 parent-child dyads to complete the research, we will potentially enroll up to 100 parent-child dyads. Because pilot studies do not provide meaningful estimates of effect sizes for between-condition comparisons, due to the imprecision inherent in data from small samples^{19,20} we base our proposed sample size of 72 parent-child dyads (36 per condition, 18 per practice) on pragmatics of recruitment, retention and the necessities for examining feasibility, providing important information for design and recruitment for the future R01 study to test the impact of Asthma Link™ in a large cluster RCT. We will identify refinements required to implement the large cluster RCT by obtaining data about several process outcomes as well as feasibility of recruitment, retention, engagement, fidelity and assessment procedures of Asthma Link™.

Taking estimation of retention rate as an illustrative outcome, and applying an intra-class (pediatric practice) correlation of 0.01, similar to the value of 0.006 from [name] prior studies of school-based teen smoking, the resulting design effect= $1.19 = 1 + [1 + 0.01 \times 9]$ ²¹ yields an effective sample size of $20/1.09 \approx 18$ dyads/condition. For a conservatively low retention rate of 80%, lower than the 97% observed in [name] previous FITLINE study,¹⁸ we can estimate a 95% confidence interval for retention percent of (51.9%, 95.7%) for each practice separately or (68.9%, 88.5%) combining all 4 practices. A sample of 18 dyads per practice (36 per condition) yields 95% confidence intervals for practice ICC of (0.018, 0.094) for a conservatively large true ICC=0.05.²² Because estimates from pilot studies alone tend to be underpowered due to the variability in estimated standard errors,^{19,20} we will combine our results (including the ICC) with clinically meaningful effect and results of previous adequately powered interventions to calculate sample size requirements for our large cluster RCT. Data from the recruited pediatric practices show that 5-7 very poorly controlled asthmatics are seen per month.

Statistical Analysis: To assess feasibility outcomes in Aim 1, we will estimate parameters relevant for planning a larger study, including standard deviations of outcomes and ICC. We will also conduct preliminary analyses of the impact of Asthma Link™ on asthma outcomes. We will compare participants in the two arms (Asthma Link™ and comparison group), using methods such as parametric or nonparametric t-test or Poisson regression, depending on the observed outcome distribution. Some outcomes may have a Poisson distribution, such as hospital admissions, while spirometry values may be continuous. Intent-to-treat and completer analyses will be performed. The data collected in this proposal will provide estimates of trial retention, ICC, standard deviation, and effect size. We will use these and data published in the literature to estimate sample size for a larger trial. The secondary outcomes analyses of asthma health outcomes will be exploratory by necessity given the pilot nature of this study.

INVESTIGATOR STUDY PLAN

Data will be collected at baseline (study entry), and at 3-, 6-, and 12-month follow-up in the privacy of the parent/child's home as the parent/child survey will be sent through email, in the pediatric practice staff's office or home (for pediatric provider and asthma champion surveys which will be sent through email), in the school nurse office or home (for school nurse surveys which will be sent through email). Assessments will be pre-tested to ensure the time burden does not exceed 30 minutes. The parent/student survey and assessment tools for this study will be adapted from [name] prior adolescent smoking cessation trials and our pre/post study^{14,18}. Data confidentiality will be emphasized on the surveys and verbally by Research Coordinator, and by the use of a unique study identification number.

Data Management: The surveys will be conducted either over the phone or by using the REDCap™ system, a nationally used secure, web-based database application (<http://project-redcap.org>) that provides: 1) an intuitive interface, 2) audit trails for tracking data manipulation and export, 3) procedures for importing data from external sources, 4) easy development of web survey tools and 5) automated export procedures to various statistical packages.

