4. OBJECTIVES*

The objective of this pilot study is to evaluate the feasibility of an implementation study of Asthma Link as an effective method of evidenced-based practice of school-supervised asthma therapy in a real-world setting. If Asthma Link is found to be an acceptable practice with appropriate adoption and sustainability, it can serve as a scalable public health model for improving asthma medication adherence and combating the significant morbidity associated with pediatric asthma in the real world, rather than just research settings.

Aim 1: We will analyze process outcomes (acceptability, adoption, costs, sustainability) of Asthma Link™ in two pediatric practices.

Aim 2: Evaluate feasibility of a cluster RCT of Asthma Link™. The *primary trial outcomes* will be participant recruitment, retention, and intervention fidelity. The *secondary trial outcomes* will be differences in the frequency of asthma symptoms, emergency department visits, hospital admissions, courses of oral corticosteroids, spirometry values and school absences between Asthma Link™ and Enhanced Usual Care sites.

As each stage of Asthma Link™ evaluation builds upon the previous stage, we will submit separate IRB amendments and proposals for each stage of this project. The data collected from the proposed study will inform a large-scale cluster RCT to test the effectiveness and implementation of Asthma Link™.

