9. STUDY TIMELINES*

Describe:

- *The duration of an individual subject's participation in the study:* 6 months
- *The duration anticipated to enroll all study subjects:* 1.5 years
- *The estimated date for the investigators to complete this study (complete primary analyses):* 3 years

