We anticipate that recruitment of n=72 dyads will take 18 months based on [name] FITLINE study ¹⁸. We do not anticipate issues with this recruitment based on prior recruitment of families for Asthma Link™ from the Worcester community in our pre/post study and based on prior recruitment from these same pediatric practices in the FITLINE study. (also see page 19 which describes estimated number of asthmatics in proposed Pediatric practices, demonstrating feasibility of recruitment). The Institutional Review Board will review all research procedures and protocols. All instruments will be submitted to the IRB for review and approval prior to use.

We will not enroll any participants in the study prior to receiving IRB approval.

SURVEY – PARENT AND CHILD – 20 MINUTES _See uploaded parent baseline, parent 3 month, parent 6 month, and parent 12 month surveys.

The 4 parent surveys will include the following constructs: Patient Health Outcome questions including the Asthma Control Test (ACT; measure of severity of asthma symptoms) and the Maximum Asthma Symptom Days (MSD), Emergency Department visits, hospital admissions, school absences, oral steroid usage and pharmacy refill data. The Baseline survey will include demographic questions that ask about the parent's age, sex, race/ethnicity, relation to the child participating in the study, education, marital status, tobacco usage, health insurance, contact information, family functioning, comorbidities, income, and average monthly as a proxy for socioeconomic status. The 3 month, 6 month, and 12 month follow up surveys for the Asthma Link™ condition will also include the following constructs: acceptability, cost, and sustainability. All surveys will be completed either on-line using RedCap (Please see data management) or over the phone with the Research Coordinator. We are using emails and/or phone calls to deliver/collect these surveys. As soon as the baseline survey has been completed, those completing the survey via email will be automatically sent out future surveys.

SURVEY – SCHOOL NURSE – 10 MINUTES _See uploaded school nurse baseline and end-of-intervention surveys.

The school nurse survey will include the following constructs: acceptability, cost, and sustainability. All surveys will be completed either on-line using RedCap (Please see data management section) or over the phone with the research coordinator. We are using emails and/or phone calls to deliver and collect these surveys.

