25. LOCAL NUMBER OF SUBJECTS

200 parents and children in grades 1-12 (aged 6-17 years) (i.e. 100 parent-child dyads total) with asthma will be recruited from the practices (25 parent-child dyads/practice) to achieve a retention of N=144 parents and children (i.e. 72 parent-child dyads) at the end of the study (from the 4 practices) at 12 month follow-up.

If two siblings are eligible for Asthma Link and this study, both children may participate in Asthma Link clinical program but only one child per family may be allowed to participate in the research study. We will grant the parent/guardian permission to choose which child they would like to participate in the research arm of the study.

Up to 16 Pediatric providers participating in Asthma Link™ will be recruited from the participating practices to participate in this study.

Up to 50 School nurses participating in Asthma Link™ will be recruited from the schools that the children participating in the study attend to participate in this study.

Up to 4 Asthma Champions participating in Asthma Link™ will be recruited from the participating practices to participate in this study.

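### The number 72 is the recruitment target in Section 11 but the completer target in Sections 13 and 25, Section 24 argues for 52 or 40, and the design-effect line uses 10 per practice instead of 18

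*Combined protocol and SAP*

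**What the plan says.** Section 4 states that the primary trial outcomes "will be participant recruitment, retention, and intervention fidelity". The plan then gives the size of the trial in several ways.

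- **Section 11 (Procedures Involved):** recruitment continues "until the target n=72 parent-child dyads (18 per site) are recruited. (see section 13 on" the sample size calculation). It adds: "We anticipate that recruitment of n=72 dyads will take 18 months".
- **Section 13 (Data Analysis and Management):** "In order to obtain a sample size of 72 parent-child dyads to complete the research, we will potentially enroll up to 100 parent-child dyads". The same section describes the 72 as 36 per condition and 18 per practice.
- **Section 25 (Local Number of Subjects):** 100 dyads will be recruited, that is "25 parent-child dyads/practice) to achieve a retention of N=144 parents and children (i.e. 72 parent-child dyads) at the end of the study".
- **Section 24 (Local Recruitment Methods):** feasibility is argued first for 13 families per practice and then for 40 children drawn from about 1,119.
- **Section 9 (Study Timelines):** the entry for "The duration anticipated to enroll all study subjects" is 1.5 years.

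Section 13 also gives precision figures for retention. It takes an intra-class correlation (ICC) of 0.01, prints a design effect of 1.19 with a multiplier of 9, and divides 20 by 1.09 to obtain about 18 dyads per condition. It then reads "For a conservatively low retention rate of 80" per cent, with 95% intervals of 51.9% to 95.7% for one practice and 68.9% to 88.5% for all four.

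**The concern.** A feasibility trial is judged on whether it enrols and keeps the number it set out to enrol and keep. Here 72 is both the number at which recruitment stops and the number expected to finish. These cannot both hold unless nobody drops out. Section 24 supports neither figure.

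Two things are at stake. First, a team that follows Section 11 literally stops too early for the completer target in Sections 13 and 25. Second, the plan offers no recruitment benchmark apart from these totals, so the same result could later be reported as full success or as a clear shortfall. The design-effect line raises a related doubt, because its cluster size and arm size are not those of the trial described in the same section.

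**Working it through.** **Inputs.** 72 recruited (Section 11); 72 completing and up to 100 enrolled (Section 13); 25 per practice, 100 in total, 72 retained (Section 25); 13 per practice and 40 children (Section 24); four practices, two per condition (Section 11); retention of 80%, or 97% in the cited earlier study, and ICC 0.01 (Section 13); 18 months (Sections 9 and 11).

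**1. Completers under each enrolment figure**

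| Enrolled | at 80% | at 97% |
|---|---|---|
| 72 | 72 × 0.80 = 57.6 | 72 × 0.97 = 69.8 |
| 100 | 100 × 0.80 = 80 | 100 × 0.97 = 97 |

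At 80%, 72 completers need 72/0.80 = 90 enrolled. Retaining 72 of 100 is 72%, which is below the 80% that Section 13 regards as conservative.

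**2. The same 72 enrolled against each stated total**

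- Section 11: 72/72 = 100%
- Section 25: 72/100 = 72%
- Section 24, first figure: 13 × 4 = 52, and 72/52 = 138%
- Section 24, second figure: 72/40 = 180%

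**3. Recruitment rate.** 72/18 = 4.0 a month; 100/18 = 5.6 a month. Section 13 reports that "5-7 very poorly controlled asthmatics are seen per month". Over 18 months that is 5 × 18 = 90 to 7 × 18 = 126 if it is the total for all practices, or 360 to 504 if it is per practice (× 4). The text does not say which. These counts are before refusals, but eligibility is wider than this group. The window is therefore not shown to be too short.

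**4. Design effect, 1 + (m − 1) × ICC.** The plan's figure reproduces only with m = 10 and 20 per condition: 1 + 9 × 0.01 = 1.09, and 20/1.09 = 18.3. With the numbers the plan gives elsewhere:

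| Per practice | Per condition | Design effect | Effective n per condition |
|---|---|---|---|
| 18 | 36 | 1 + 17 × 0.01 = 1.17 | 36/1.17 = 30.8 |
| 25 | 50 | 1 + 24 × 0.01 = 1.24 | 50/1.24 = 40.3 |

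The printed 1.19 does not agree with the 1.09 used. That may be a fault in the extracted text, but the 9 and the 20 do not depend on it.

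**5. Retention intervals (exact, Clopper-Pearson).** The printed pooled interval is the one for 80% of 72 (57.6/72: 68.9 to 88.5). It carries no design effect, and it treats 72 as the number enrolled. With the design effect:

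- 72 enrolled, 72/1.17 = 61.5 effective: 67.9 to 89.1
- 100 enrolled, 100/1.24 = 80.6 effective: 69.6 to 88.1
- 100 enrolled, 72% retention: 60.9 to 81.4

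The printed single-practice interval is the one for 12/15 (51.9 to 95.7), yet no section plans 15 per practice. Whole counts give 52.4 to 93.6 (14/18), 58.6 to 96.4 (15/18) and 59.3 to 93.2 (20/25).

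**The case against.** The strongest reply is that the intended design can be recovered. Sections 13 and 25 agree with each other, Section 11 refers the reader to Section 13, and only the wording of Section 11 and the older-looking figures in Section 24 disagree. This stands in part: stopping at 72 is a risk and not a certainty. It does not remove the conflict, because Section 11 is the operational instruction and says that recruitment ends at 18 recruited per site.

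A second reply is that Section 13 sets 100 as a ceiling, so 72% is not a planned retention rate. That is fair for Section 13, since 90 enrolled would suffice at 80%. Section 25, however, says that 100 will be recruited.

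Third, Section 10 measures recruitment by counts screened, eligible and refusing, not as a percentage of target, and no go/no-go rule uses these totals. That is correct. The percentages in the working show how ambiguous the benchmark is; they are not an error in a decision rule.

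Fourth, Section 9 gives 1.5 years for all subjects, which could be read as covering 100. Section 11 nevertheless ties the same 18 months to 72.

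Fifth, the precision errors change little. The sample size rests on pragmatic grounds, retention is only an illustration, the effective size of 18 does not generate the printed intervals, and the corrected value is larger. All of this stands. The origin of the 15 is also unknown. It may be 18 divided by the design effect (18/1.17 = 15.4; 18/1.19 = 15.1) and rounded, but the plan does not say so. If so, a between-practice design effect would not apply within a single practice.

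**Conclusion.** The inconsistency is real and should be corrected. The plan has four recruitment figures (72, 100, 52 and 40), and 72 serves both as the number enrolled and as the number completing. On the plan's own retention rates, enrolling 72 yields about 58 to 70 completers, not 72. The consequence is an unclear benchmark for recruitment and an unclear denominator for retention, both primary outcomes. Retention can still be estimated validly on whatever number is enrolled.

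The design-effect line describes a trial of 10 per practice, hence 10 × 4 = 40 dyads. That matches the 40 children in Section 24, so both look like remnants of a smaller design; this is an inference. The correction raises the effective size from 18 to 30.8 or 40.3 per condition and moves the pooled limits by about 1 percentage point or less at 80% retention. It is minor.

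These results assume the plan's ICC of 0.01, its retention rates of 80% and 97%, and equal numbers per practice.

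**What to change.** State one enrolment target and one completer target, and use them throughout. The simplest course is to keep Section 25 and align the rest with it.

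- **Section 11:** say that up to 100 dyads (25 per practice) will be enrolled so that 72 (18 per practice) complete the 12-month follow-up.
- **Section 24:** replace 13 families per practice and 40 children with 25 and 100, once the investigators confirm that they can support the feasibility statement at that number.
- **Section 13, target:** say whether 100 is a ceiling with margin (80 completers at 80%; 90 would be enough) or the number needed at 72% retention.
- **Sections 9 and 11:** confirm or restate the 18 months for 100 dyads, about 5.6 a month. In Section 13, say whether the 5 to 7 patients a month are per practice or in total.
- **Section 13, precision:** with 100 enrolled, give a design effect of 1.24, an effective size of 40.3 per condition, a pooled interval of 69.6% to 88.1% at 80% retention (60.9% to 81.4% at 72%), and a single-practice interval of 59.3% to 93.2% (20/25, no design effect).

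If the sponsor instead means 72 enrolled, Sections 13 and 25 must change, and the figures are 1.17, 30.8, 67.9% to 89.1%, and 52.4% to 93.6% (14/18). Only the set for the chosen target should appear.

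The cost is wording and arithmetic in Sections 11, 13 and 24 and a check of the timeline. Nothing exceeds the 100 dyads already allowed. If the budget was built on 72, the 28 further dyads would add 28 × $130 = $3,640 in gift cards ($30 + $30 + $30 + $40 per dyad, Section 24) plus coordinator time.
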